2.1 OBJECTIVES AND SCIENTIFIC AIMS

Part I: Phase I Dose-Escalation of DS-3201b in Combination with Irinotecan

Primary Objectives

- To assess the safety, tolerability, and maximum tolerated dose (MTD) of DS-3201b in combination with fixed-dose irinotecan in patients with recurrent small cell lung cancer (SCLC).
- To determine the recommended phase II dose (RP2D) of DS-3201b in combination with irinotecan in patients with recurrent SCLC.

Secondary Objectives

- To assess the plasma pharmacokinetics (PK) after a single dose of DS-3201b in combination with irinotecan.

Part II: Phase II Study of DS-3201b in Combination with Irinotecan

Primary Objectives

- To determine the objective response rate (ORR) to treatment with DS-3201b at the RP2D in combination with irinotecan in patients with recurrent SCLC.

Secondary Objectives

- To determine the progression-free survival and overall survival of patients with recurrent SCLC treated with DS-3201b in combination with irinotecan.
- To determine the duration of response or duration of stable disease in patients with recurrent SCLC treated with DS-3201b in combination with irinotecan.
- To explore SLFN11 expression by immunohistochemistry as a potential predictive biomarker of response to DS-3201b and correlate with trimethylation of H3K27 as measured by immunohistochemistry in pretreatment, on-treatment and post-treatment tissue samples as well as in circulating tumor cells (CTCs)
- To explore changes in the genomic landscape of pre-treatment, on-treatment and post-treatment tumor tissue using bulk RNA sequencing.
- To assess the plasma pharmacokinetics (PK) after a single dose of DS-3201b in combination with irinotecan.

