
6.1 CRITERIA FOR SUBJECT ELIGIBILITY

6.2 Subject Inclusion Criteria

- Signed informed consent form (ICF)
- Ability to comply with the study protocol as per the investigator's judgment
- Age \geq 18 years at the time of signing the ICF
- Life expectancy \geq 12 weeks
- Karnofsky performance status \geq 70% or ECOG 0, 1 or 2.
- Pathologically confirmed diagnosis of small cell lung cancer. Patients with a diagnosis of combined small cell lung cancer with other histologies may be considered for

inclusion if the predominant histology is SCLC and only after discussion with the study PI. Patients with transformed SCLC from NSCLC are allowed on study after discussing with the MSKCC or JHU Study PI.

- Radiographically documented progression of disease after prior treatment with a platinum doublet regimen. Patients who received a platinum doublet regimen in combination with immunotherapy are still eligible for the study.
- Measurable disease according to RECIST v1.1
- Adequate tissue sample available for both IHC testing of IHC testing of SLFN11 and H3K27me3 and molecular profiling (archived tissue block or 20 unstained slides). Tissue sample can be either from an initial pre-platinum-based chemotherapy sample OR from a repeat biopsy sample after progression on platinum-based chemotherapy.
- Concurrent consent to the appropriate biospecimen research protocols at MSKCC (#06-107 Storage and Research Use of Human Biospecimens) and at JHU.
- Adequate hematologic and end-organ function, as defined by the following laboratory test results obtained within 14 days prior to initiation of study treatment:
 - Adequate bone marrow function as defined by:
 - Absolute neutrophil count (ANC) $\geq 1.5 \times 10^9/L$ ($1500/\mu L$) without granulocyte colony-stimulating factor support within 2 weeks prior to starting study therapy
 - Hemoglobin $\geq 9 \text{ g/dL}$ (transfusions to meet this criterion are allowed)
 - Platelets $\geq 150 \times 10^9/L$ without transfusion
 - Adequate renal function as defined by:
 - Creatinine clearance $\geq 30 \text{ mL/min}$ as calculated using the modified Cockcroft-Gault equation or Modification of Diet in Renal Disease (MDRD) formula OR serum creatinine $\leq 1.5 \times \text{ULN}$
 - Adequate hepatic function as defined by:
 - AST, ALT, and alkaline phosphatase (ALP) $\leq 3 \times \text{ULN}$ with the following exceptions:
 - Patients with documented liver metastases: AST, ALT and ALP $\leq 5 \times \text{ULN}$

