8.1 PRETREATMENT EVALUATION

To be completed upon acceptance signature on ICF and within 28 days of initiating treatment (unless a different timeframe is required per the specific item):

- History and physical examination (including patient characteristics)
- Concomitant medications
- Clinical examination (including tumor assessment)
- ECOG Performance Status
- Serum pregnancy test for women of childbearing potential (obtained at baseline)
- Serum or urine pregnancy test for women of childbearing potential (needs to be obtained on the start date of each treatment cycle)
- Blood biochemistry and complete blood count (CBC), needs to be within 14 days of initiating treatment
- Comprehensive metabolic panel
- Urinalysis
- ECG. 12-lead electrocardiogram for measurement of corrected QT interval according to the Fridericia formula: electrocardiogram must be registered at rest. For any EKG assessment, if the initial EKG shows a prolonged QTc, then two additional EKGs will be obtained, resulting in three specimens taken after a space of 1 minute, and the mean of the 3 EKGs will be used to determine eligibility and for grading of TRAEs.
- Hepatitis B testing (HBV surface antigen and core antibody) if not previously performed (at any time)
- Hepatitis C testing (HCV antibody) if not previously performed (at any time)
- HIV antibody testing if not previously performed (at any time)
- CT scan of chest, abdomen and pelvis with and without IV contrast
 - For patients with allergy to iodinated IV contrast, pre-medication with steroids is acceptable. Alternatively, MRIs with and without contrast can be obtained.
- Brain MRI with and without IV contrast
- IHC testing of SLFN11 and H3K27me3 of any tumor tissue obtained prior to treatment with DS-3201b.
- Confirmation of sufficient pre-treatment tissue for correlative analyses using bulk RNA sequencing. Archival tissue may be used. If there is insufficient tissue for bulk RNA testing (testing requires 20 unstained slides or a paraffin block), then a repeat biopsy will be required prior to the initiation of study treatment.

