10.1 EVALUATION DURING TREATMENT/INTERVENTION

Each cycle will consist of 21 days. All assessments, imaging and procedures will be performed within a window of $+\text{-} 4$ days (with the exception of the pharmacokinetic assessments). The following assessments will apply to all patients enrolled in both the Phase I and Phase II portions of the study.

Table 3.0 Study Assessments.

	Baseline Labs ¹	Safety Run-In for DS-3201b	Cycle 1			Cycle 2		Cycle 3+		EOT
		7 days prior to C1D1 (C1D-7)	Day 1	Day 8	Day 15	Day 1	Day 8	Day 1	Day 8	
Informed consent	X									
History, physical exam, (including vital signs and performance status)	X	X	X	X	X	X	X	X	X	X
Medication review (both prior and concomitant)	X	X	X	X	X	X	X	X	X	X
Adverse events monitoring (both serious and all others)	X	X	X	X	X	X	X	X	X	X
Serum or urine pregnancy test (for women of childbearing potential). Serum test only at screening.	X (serum)	X	X			X		X		
CBC with differential	X	X	X	X	X	X	X	X	X	X
Comprehensive metabolic panel ²	X	X	X	X	X	X	X	X	X	X
Urinalysis with microscopic analysis ³	X		X			X		X		X
EKG	X		X	X		X	X	X	X	X
Hepatitis B, Hepatitis C and HIV antibody testing	X (if not done prior)									
Coagulation profile including fibrinogen	X									
Lipid profile	X									
CT chest abdomen and pelvis with contrast ⁴	X							X ⁴		
Brain MRI with and without contrast ⁴	X							X ⁴		
Research bloods for PDX engrafting in [name] Lab (MSK)		X				X				X

main campus patients only) ⁵										
Research bloods for circulating tumor cell (CTC) analyses with EPIC Sciences ⁶	X	X	X	X	X	X	X	X		X
Research bloods for cfDNA banking at MSKCC ⁷	X	X	X	X	X	X	X	X		X
Tissue sample for study correlates (archival or fresh tissue) ⁸	X									
Tissue sample for study correlates (fresh biopsy only) ⁸								X		X ⁹
DS-3201b Administration (daily)		X	X	X	X	X	X	X	X	
Irinotecan administration (Days 1 and 8 only)			X	X		X	X	X	X	
PK assessment ¹⁰		X	X	X	X	X				

¹ All baseline testing needs to be obtained with 28 days of starting therapy. Exceptions include CBC, CMP, coagulation profile including fibrinogen, which must be obtained within 14 days.

² Includes electrolytes, BUN/creatinine, sodium, potassium, chloride, carbon dioxide, BUN/creatinine, calcium, glucose, AST, ALT, alkaline phosphatase, total bilirubin, direct bilirubin, albumin, total protein, magnesium, phosphorus, LDH.

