³ Urinalysis will include assessments of turbidity and color, pH, specific gravity, protein, ketones, bilirubin, occult blood, nitrite, glucose, and leukocyte esterase. Urine microscopic analysis will include erythrocytes, leukocytes, bacteria, casts, and crystals.

⁴ CT scans and brain MRIs will be obtained at the completion of every 2 cycles (approximately every six weeks).

⁵ CTCs for PDX engrafting will only be collected from samples from patient's treatment at MSKCC main campus. Due to feasibility barriers with transporting samples, no patient samples from MSKCC Regional Care Centers or from JHU will be collected for this purpose. Each sample will include two 10 cc EDTA tubes to be transported on ice.

⁶ CTCs for analysis by EPIC Sciences will be collected from all MSKCC sites and all JHU sites. Each sample will include one 10 cc Streck tube to be transported at room temperature.

⁷ CTCs for banking at MSKCC will be collected from all MSKCC sites and all JHU sites. Each sample will include one 10 cc Streck tube to be transported at room temperature.

⁸ Any fresh tissue biopsy will be performed ONLY if deemed medically safe by the institutional PI. There will be a window of +/- 4 days for the biopsy. The pre-treatment tissue sample can be archival if there is adequate tissue.

⁹ Post-progression tissue biopsy is OPTIONAL.

¹⁰ PK draws: There is a \pm 15-minute window for PK blood draws. PK assessments will be obtained in both Phase I and Phase II. Please see Table 4 for the complete PK schedule. Each PK blood draw will include 5 cc of blood collection.

Table 4.0 Pharmacokinetics (PK) Schedule for DS-3201b (Phase I and Phase II)

Cycle and Day	Time point						
7 days prior to C1D1	0.5-hour post-dose	1-hour post-dose	2-hour post-dose	4-hour post-dose	6-hour post-dose	8-hour post-dose	
Cycle 1 Day 1	Pre-dose	0.5-hour post-dose	1-hour post-dose	2-hour post-dose	4-hour post-dose	6-hour post-dose	8-hour post-dose
Cycle 1 Day 8	Pre-dose						
Cycle 1 Day 15	Pre-dose	0.5-hour post-dose	1-hour post-dose	2-hour post-dose	4-hour post-dose	6-hour post-dose	8-hour post-dose
Cycle 2 Day 1	Pre-dose						

Correlative Studies:

Studies Using Tumor Tissue:

We will obtain mandatory on-treatment core biopsies at Cycle 3 Day 1 +/- 4 days. The Cycle 3 Day 1 biopsy may be canceled if deemed medically unsafe (e.g., prior biopsy resulting in pneumothorax or other complication, bleeding diathesis, etc.) by the PI. The end of trial (EOT) biopsy will be optional.

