The ORR is defined as the proportion of patients with CR, or PR at any reassessment after start based on RECIST v1.1 criterion. The time frame for evaluating the primary endpoint of ORR for this portion of the study will be 6 months from the date of Cycle 1 Day 1 for each patient. The ORR and corresponding exact 95% CI will be reported. Progression-free survival will be measured from the start of treatment until the documentation of disease progression or death due to any cause, whichever occurs first, and censored on the date of last tumor assessment. In addition, we will document absence of tumor progression for patients who are still alive prior to data cutoff, dropout, or the initiation of alternate anticancer treatment. Overall survival will be determined as the time from the start of DS-3201b treatment to death, and censored on the last follow-up date. PFS and OS will be evaluated using the Kaplan-Meier method. The duration of response (for those with CR or PR) and durable of stable disease while on treatment (for those with SD) will also be evaluated using the Kaplan-Meier method.

All recorded toxicity data and adverse events of DS-3201b will be listed and tabulated by system organ class, preferred term and treatment. Any significant vital signs and clinical laboratory test results will be listed and summarized. Any significant physical examination findings and clinical laboratory results will be listed.

As secondary objectives, we will explore downstream mechanistic biomarkers of DS-3201b including SLFN11 expression and H3k27me3 signature by descriptive and graphical summaries of assays performed on tissue samples obtained during the study. The Wilcoxon rank sum test will be used to assess SLFN11 expression by immunohistochemistry as a potential predictive biomarker of response to DS-3201b and to correlate with trimethylation of H3K27 as measured by immunohistochemistry in pretreatment, on-treatment and post-treatment tissue samples as well as in circulating tumor cells (CTCs). In addition, next-generation sequencing (NGS) will also be performed on pre-treatment, on-treatment and post-treatment tissue samples obtained from the study. This data will be analyzed using descriptive

and graphic summaries of the assays performed, including use of gene expression heat maps and advanced computational biostatistics with collaborators in the [name] laboratory.

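### Section 14.0 names the rank sum test to correlate SLFN11 with H3K27me3, but states no split, cut-off or coefficient, so the named test gives no correlation estimate (low severity).

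*Combined protocol and SAP*

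**What the plan says.** Section 14.0 (Phase II, secondary biomarker analyses) gives one test two tasks in a single sentence. The first task: "The Wilcoxon rank sum test will be used to assess SLFN11 expression by immunohistochemistry as a potential predictive biomarker of response to DS-3201b". The second is "to correlate with trimethylation of H3K27 as measured by immunohistochemistry in pretreatment, on-treatment and post-treatment tissue samples", and the sentence then extends this to circulating tumor cells. Relating the two markers is part of a Phase II secondary objective (Sections 1.0 and 2.1), which is worded as exploratory.

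The sentence before it in Section 14.0 plans descriptive and graphical summaries of both markers. Section 12.0 likewise says that correlative results will be reported descriptively and points to Section 10.0.

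Section 10.1 covers collection, assays and a hypothesis: on treatment, SLFN11 should rise and H3K27me3 should fall. On-treatment tissue is due at Cycle 3 Day 1, but "The Cycle 3 Day 1 biopsy may be canceled if deemed medically unsafe". For post-treatment tissue, "The end of trial (EOT) biopsy will be optional". Table 3.0 schedules "Research bloods for circulating tumor cell (CTC) analyses with EPIC Sciences" at repeated visits. Before treatment, Section 6.2 requires "Adequate tissue sample available for both IHC testing of IHC testing of SLFN11 and H3K27me3 and molecular profiling"; the sample may predate platinum therapy or be a biopsy taken after progression on it.

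**The concern.** For SLFN11 against response, the two groups are supplied: responders (CR or PR) and everyone else. For SLFN11 against H3K27me3 there are two scores from the same specimen and no groups. A rank sum test cannot be run on that question until one marker is cut into two classes. The plan does not say which marker, at what value, in which specimen, or whether the sample times are analysed separately or as change.

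At stake is a secondary objective that would be reported without an estimate of the association, possibly with less power than the same data allow. The p-value would also depend on choices that the plan leaves open. The response-rate test, the sample size and the stopping rules do not depend on any of this.

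**Working it through.** The documents state no power, alpha or sample size for this analysis, so there is no planned figure to reproduce. The check is first textual, then illustrative.

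**1. What the named test computes.** With n1 and n2 specimens in two groups and R1 the rank total of group 1, U = R1 - n1(n1+1)/2. U/(n1·n2) estimates the chance that a score from group 1 exceeds one from group 2. A group label is needed for every specimen, and the result is not a correlation coefficient.

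**2. Where a label could come from.**

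| Question | Groups | Source |
|---|---|---|
| SLFN11 v response | CR/PR v not | response definition, Section 14.0 |
| SLFN11 v H3K27me3 | none | Sections 6.2, 8.1, 10.1, 12.0 and 14.0 give no split, IHC score, cut-off or coefficient |

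The sample times are listed and scheduled. How they enter the analysis is not stated.

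**3. Power at one sample time.** Inputs: N=16 and N=31, the Phase II accrual limits in Section 14.0, so these are the most pairs available. Assumptions: one pair of scores per patient, bivariate normal scores, two-sided 0.05. Spearman: r = 1 - 6Σd²/[N(N²-1)], with t = r·sqrt[(N-2)/(1-r²)] on N-2 degrees of freedom. Rank sum: exact test of H3K27me3 between SLFN11 groups split at the median. Simulated power (5,000 runs; the -0.5 row was confirmed in repeat runs):

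| True correlation | N=16: Spearman v rank sum | N=31: Spearman v rank sum |
|---|---|---|
| -0.3 | 19% v 14% | 35% v 25% |
| -0.5 | 46% v 32% | 78% v 60% |
| -0.7 | 83% v 63% | 99% v 93% |

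With zero correlation, both tests reject in about 5% of runs.

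**4. Dependence on the score scale.** The documents do not give the scale. At -0.5:
- With 40% to 60% of SLFN11 scores at the floor and the split made there, Spearman v rank sum is 38-43% v 29-31% at N=16 and 65-76% v 58-61% at N=31.
- With SLFN11 scored only present/absent, it is 33-34% v 29-30% at N=16 and 60-61% v 59-60% at N=31.

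Part of the N=16 gap in both bullets arises because Spearman used approximate p-values and rank sum exact ones. With no association, the rejection rates were 5.2-5.8% and 4.0-4.6%.

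**5. Effect of an open cut-off.** Take no association and split H3K27me3 at the 25th, 50th or 75th percentile. Each cut alone rejects in about 4-5% of runs. Keeping the best of the three rejects in about 10% (N=16) or 11% (N=31).

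**6. What an estimate would show.** Take an observed Spearman correlation of -0.5, and use Fisher z with SE = sqrt[(1 + r²/2)/(N-3)].
- N=16: SE = sqrt(1.125/13) = 0.294; z = -0.549 ± 1.96 × 0.294; 95% CI -0.81 to 0.03.
- N=31: SE = sqrt(1.125/28) = 0.200; z = -0.549 ± 1.96 × 0.200; 95% CI -0.74 to -0.16.

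These intervals show how little the data could settle, and the named test would not report them.

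**The case against.** The best defence is that little rests on this test. The objective is exploratory, descriptive and graphical summaries are planned for the same markers, and no decision or error rate depends on the result. Splitting IHC scores is also a recognised practice, and with present/absent scoring the power argument nearly disappears at N=31. All of this stands, and it fixes the severity at low. It does not supply the missing groups, and the summaries as described commit to no measure of association.

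Some stronger inferences are tempting, and the documents do not support them.
- A reader might infer that the split and sample time will be picked after the data are seen. The plan is silent, so they could be. Appendix C (Lab Manual) is listed but its text is not in the documents; it might hold scoring rules, although it would not normally set the statistical method.
- A reader might infer that serial tissue or CTC samples will be pooled as if independent, or that every sample time will be tested in turn. The plan proposes neither.
- A reader might infer that pretreatment tissue must lead, because eligibility secures it for every patient. Completeness is an advantage, but the sample may come from before platinum or after progression on it. By the protocol's own rationale (Sections 3.3 and 3.5), SLFN11 can be silenced between those two points. Pretreatment tissue alone also says nothing about the treatment-induced change hypothesised in Section 10.1.

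**Conclusion.** The point holds at low severity. The method named for SLFN11 against H3K27me3 does not match the stated purpose: it needs two groups that the plan does not define, and it returns no correlation. This is a mismatched method with a ready replacement, not only missing detail.

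The possible cost in power is about 14 percentage points at N=16 (46 - 32) and 18 at N=31 (78 - 60). Those figures assume continuous scores, a true correlation of -0.5, a median split and a pair of scores from every patient. The loss is smaller with many floor values and close to nil at N=31 with present/absent scoring. The correlation, score scale and number of evaluable pairs are assumptions; the documents give none of them. The rank sum test for SLFN11 by response is appropriate, and the primary analysis is untouched.

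**What to change.** In Section 14.0:
- Keep the rank sum test for SLFN11 in responders versus non-responders.
- For SLFN11 against H3K27me3, replace it with a Spearman (or Kendall) rank correlation and 95% CI within each sample time, separately for tissue and CTCs. State that serial samples from one patient are not pooled as independent.
- For the hypothesised treatment effect, correlate the paired changes in the two markers from pretreatment to Cycle 3 Day 1, in patients with both samples, and report how many that is.
- Label these estimates descriptive, or name one lead sample time of the sponsor's choice.

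The cost is a few sentences in Section 14.0. The samples, assays, visits and sample size stay the same.

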15.1 RESEARCH PARTICIPANT REGISTRATION AND RANDOMIZATION PROCEDURES

15.2 Research Participant Registration

Confirm eligibility as defined in the section entitled Inclusion/Exclusion Criteria. Obtain informed consent, by following procedures defined in section entitled Informed Consent Procedures. During the registration process registering individuals will be required to complete a protocol specific Eligibility Checklist. The individual signing the Eligibility Checklist is confirming whether or not the participant is eligible to enroll in the study. Study staff are responsible for ensuring that all institutional requirements necessary to enroll a participant to the study have been completed. See related Clinical Research Policy and Procedure #401 (Protocol Participant Registration).

15.3 Randomization

This is a multicenter, Phase I/II non-randomized, single-arm study.

16.1 DATA MANAGEMENT ISSUES

A Clinical Research Associate (CRA), Regulatory Research Associate (RRA) and Clinical Research Coordinator (CRC) will be assigned to the study. The responsibilities of these staff members include project compliance, data collection, abstraction and entry, data reporting, regulatory monitoring, problem resolution and prioritization, and coordinating the activities of the protocol study team.

The data collected for this study will be entered into a secure database (Medidata). Source documentation will be available to support the computerized patient record. The principal investigator will maintain ultimate responsibility for the clinical trial. Data from JHU will be entered into the Medidata database maintained by MSKCC.

FDA regulations require that records and documents pertaining to the conduct of clinical trials and the distribution of investigational drug, patient records, consent forms, laboratory test results, and medication inventory records, must be retained for 2 years after the last marketing application approval in an ICH region or after at least 2 years have elapsed since formal discontinuation of clinical development of the investigational product. All state and local laws for retention of records also apply.

